## Attachment 1: Lower-dose prophylactic anticoagulation

For prophylactic anticoagulation, the following doses should not be exceeded:

### UFH:

- 5.000 - I.U. every 8 or 12 hours or
- .7500 I.U. every 12 hours
- Maximal cumulative dose of 15.000 I.U. when infused continuously i.v. over 24 hours

### LMWH:

#### Enoxaparin

- 40 mg every 24 hours or 30mg every 12 hours s.c. or
- 40 mg every 12 hours s.c. for weight >150kg or BMI >40-50 or
- 60 mg every 12 hours s.c. for BMI >50

#### Dalteparin

- 5.000 I.U. every 24 hours s.c.

#### Nadroparin

- for patients  $\leq$  70kg 3.800 I.U. every 24 hours s.c.
- for patients > 70kg 5.700 I.U. every 24 hours s.c.

#### Tinzaparin

- 3.500 I.U. every 24 hours s.c.

#### Certoparin

- 3.000 I.U. every 24 hours s.c.

#### Reviparin

- 1.750 I.U. every 24 hours s.c.

## **Attachment 2: Seven category ordinal scale recommended by the WHO (23-25)**

---

7: Death

---

6: ICU, requiring invasive mechanical ventilation

---

5: ICU, not requiring invasive mechanical ventilation

---

4: Non-ICU, requiring oxygen

---

3: Non-ICU, not requiring oxygen

---

2: Discharged without resumption of normal activities

---

1: Discharged with resumption of normal activities

---

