- D-Dimer elevation above 750 µg/L in patients 50 years of age or younger.
- In patients older than 50 years an age-adjusted cut-off will be calculated using the following formula:  $15 \times \text{Age } \mu\text{g/L}$ .

Any patient with a medical condition that requires use of any therapeutic parenteral or therapeutic oral dose anticoagulation (e.g. atrial fibrillation) is not eligible for participation. Moreover, patients at particularly increased risk of bleeding and those using medications that might interact with the study drug will be excluded.

Subjects with moderate to severe respiratory symptoms, tested positive for SARS-CoV-2, can be enrolled into the study, if the subjects meet all of the inclusion and none of the exclusion criteria. The

subjects will be randomly assigned to receive treatment with rivaroxaban or SOC with prophylactic LMWH or UFH.

Randomization can occur during the hospital stay or out-of-hospital, if admission to the hospital is not necessary, whatever the treating physician judges. Randomization should not occur later than 3 days after screening. Subjects will be randomized by strata including site, gender (male, female, diverse), age (< 65 versus  $\geq 65$  years), kidney function ( $eGFR \geq 30$  mL/min/1.73m^2 and < 50 mL/min/1.73m^2 versus  $eGFR \geq 50$  mL/min/1.73m^2), history of CAD or heart failure (yes/no), oxygen demand on admission to the hospital (supplementary oxygen required versus not required) and setting (outpatients versus hospitalized patients).

After randomization, subjects will receive treatment with rivaroxaban 20 mg (15 mg for subjects with an  $eGFR \geq 30$  mL/min/1.73m^2 and <50 mL/min/1.73m^2) once daily (OD) for at least 7 days or SOC with prophylactic LMWH or UFH according to the local standards and choice of the treating physician.

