## 5. TREATMENT ALLOCATION AND BLINDING

### Treatment Allocation

#### Procedures for Randomization and Stratification

This trial is an open label study. Central randomization will be implemented in this study. Subjects will be randomly assigned to 1 of 2 treatment groups (rivaroxaban or SOC with prophylactic UFH or LMWH) in a 1:1 fashion based on a computer-generated randomization schedule prepared before the study starts under the supervision of the sponsor. Randomization will follow a dynamic randomization algorithm with residual randomness designed to minimize imbalance in terms of variance between treatments taking the following stratification factors into account: site, gender (male, female, diverse), age (< 65 versus  $\geq$  65 years), kidney function (eGFR  $\geq$  30 mL/min/1.73m^2 and < 50 mL/min/1.73m^2 versus eGFR  $\geq$  50 mL/min/1.73m^2), history of CAD or heart failure (yes/no), oxygen demand on admission to the hospital (supplementary oxygen required versus not required) and setting (outpatients versus hospitalized patients). The computer system will dictate the treatment assignment for the subject. The requestor must use his or her own user identification and personal identification number when contacting the system and will then give the relevant subject details to uniquely identify the subject.

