### **9.1.3. Treatment Phase**

#### **Randomization/Day 0**

If the subject meets all of the inclusion and none of the exclusion criteria, he or she is eligible to be randomly assigned to receive rivaroxaban or SOC with prophylactic LMWH or UFH at the Day 0 visit.

Randomization should occur no more than 3 days after the screening.

Also, before randomization occurs, site staff should review eligibility criteria, including concomitant medications administered during the index event. Attention should be paid to ensure that prohibited medications were not administered. The patient will be initially assessed according to the seven-category ordinal scale, as recommended by the WHO (Attachment 2) in order to be able to evaluate the clinical improvement during the course of the disease (23-25). The treating physician will be informed about the patient participation in the study.

After randomization, the first dose of study drug should be started on the next day or on the same day. The time of the first dose should be recorded as accurately as possible. The first dose does not need to be delayed if the last administration of prophylactic LMWH or UFH was longer than 6 hours ago. The administration date and time of the first dose of study drug will be recorded in the source document and eCRF.

During the hospital stay the subject and the hospital personal in charge of administration of drugs should be instructed on how to take the drug. They will be instructed to take the drug (rivaroxaban 20 mg OD, 15 mg OD if  $eGFR \geq 30$  mL/min/1.73m^2 and  $<50$  mL/min/1.73m^2 if randomized to the rivaroxaban arm) through discharge or until attending physician considers an adjustment in the anticoagulation needs to be made.

Patients in the out of hospital setting will receive the drug (rivaroxaban 20 mg OD, 15 mg OD if  $eGFR \geq 30$  mL/min/1.73m^2 and  $<50$  mL/min/1.73m^2 if randomized to the rivaroxaban arm) for 7 days post randomization.

Also, at the randomization visit, the importance of reporting signs and symptoms associated with bleeding, DVT and PE will be stressed.

Subjects will be counseled on the signs and symptoms associated with DVT, PE and bleeding.

For bleeding events, subjects and family members as appropriate, will be instructed:

- To seek medical attention if they develop bleeding
- To contact the investigative site staff or study investigator before the next dose of study medication is due

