### 11.2 Primary and Co-primary Efficacy Endpoints

The primary endpoint time is

- D-dimer at day 7 post randomization

The co-primary endpoint is the following:

- Seven-category ordinal scale recommended by the WHO at day 7 post randomization (Attachment 2)

The primary efficacy endpoint is D-dimer at day 7 post randomization will adjusted for baseline measurement. The logarithmic D-dimer measurements (using the natural logarithm) will be analyzed by an analysis of covariance (ANCOVA). The model will include treatment group and stratification variables of the randomization as factors and the logarithmic baseline D-dimer measurement as covariate. Least squares means for D-dimer at day 7 in the two treatment groups will be presented with 95% confidence intervals as well as the difference between the treatment groups at day 7 with 95% confidence interval and p-value testing the null hypothesis of no treatment difference, i.e. a mean difference (on the

logarithmic scale) of 0. For ease of interpretation the results will also be converted to the original measurement scale.

The co-primary endpoint is the seven-category ordinal scale recommended by the WHO (Attachment 2) at day 7 post randomization adjusted for baseline score. Frequencies and percentages of the scores at day 7 will be provided stratified by treatment group. The distributions of the scores will be compared between the two treatment groups using a nonparametric Wilcoxon (Mann-Whitney) rank-sum test stratified by baseline score dichotomized as smaller or equal 3 vs. larger 3. The treatment effect will be reported as probabilistic index or relative effect, i.e. the probability that an observation in the treatment group will be smaller (more favourable) than an observation in the control group, with 95% confidence interval.

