## 11.4 Subgroup analyses

Subgroup analyses are planned to explore a possible heterogeneity of the treatment effect concerning the following baseline characteristics: setting (outpatients versus hospitalized patients), gender, age (< 65 versus  $\geq 65$  years), kidney function (eGFR  $\geq 30$  mL/min/1.73m^2 and < 50 mL/min/1.73m^2 versus eGFR  $\geq 50$  mL/min/1.73m^2), smoking status, diabetes, presence of coronary heart disease or heart failure (yes/no), need for oxygen treatment at baseline (supplementary oxygen required versus not required), inclusion based on D-dimer, hs-cTnT or both. For subgroup analyses the respective baseline characteristic and its interaction with treatment are included in the regression models described above for the primary and secondary endpoints. Treatment effect heterogeneity across subgroups will also be visually inspected in forest plots.

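### The co-primary scale gives never-admitted outpatients no recovery category, which dilutes the co-primary effect by an amount that depends on an unstated outpatient share

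*Protocol*

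**What the plan says.** Protocol section 3.1 (and the Synopsis) opens the trial to patients who are not admitted: "Randomization can occur during the hospital stay or out-of-hospital, if admission to the hospital is not necessary". Section 9.1.3 has its own treatment paragraph for patients outside hospital, section 5 makes setting a factor in the dynamic randomisation, and section 11.4 makes it a planned subgroup.

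The co-primary endpoint is the day-7 score on the scale in Attachment 2. Its best categories are "1: Discharged with resumption of normal activities" and "2: Discharged without resumption of normal activities". The next is "3: Non-ICU, not requiring oxygen", and category 4 is the same with oxygen. Under Randomization/Day 0 in section 9.1.3, "The patient will be initially assessed according to the seven-category ordinal scale". The day-7 visit, which may take place out of hospital, repeats the scoring. Neither place says how to score someone who was never admitted.

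Section 11.2 treats smaller scores as more favourable and compares the arms with a "rank-sum test stratified by baseline score dichotomized as smaller or equal 3 vs. larger 3". Setting is not a stratum of that test.

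**The concern.** Categories 1 and 2 presuppose a hospital stay that has ended. The only category whose words fit a never-admitted patient without oxygen is 3, at baseline and again at day 7. Three consequences follow from the literal reading.

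- A recovered outpatient scores 3, while an inpatient discharged by day 7 scores 1 or 2.
- An outpatient who had to be admitted after randomisation (section 6 foresees this) and is discharged by day 7 also scores 1 or 2. The worse course gets the better score.
- An outpatient admitted to an ordinary ward without oxygen stays at 3, so that worsening is not seen.

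The co-primary hypothesis in section 2.2 is improvement in category. In a group that the trial chose to enrol, improvement below 3 cannot be recorded. The split at baseline score 3 does not help, because outpatients without oxygen and ward patients without oxygen fall in the same stratum. The outpatient subgroup (11.4) and the longitudinal ordinal model (11.3) inherit the problem.

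**Working it through.** **1. The plan's own figure.** Section 11.7 gives 40 per group, two-sided alpha 0.05 and 80% power for a relative effect p1 = 0.68. Noether's formula with 1:1 allocation gives

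N = (1.960 + 0.842)² / [12 × 0.25 × (0.68 − 0.50)²] = 7.849 / 0.0972 = 80.7.

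Power at N = 80 is Φ(√(12 × 0.25 × 80) × 0.18 − 1.960) = Φ(2.789 − 1.960) = 79.6%. The stated figure reproduces, so the sample-size arithmetic is sound.

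**2. What the coding does.** Let *literal* mean that every never-admitted outpatient whose true state is 1, 2 or 3 is scored 3, with 4 to 7 unchanged. Let *recoded* mean that recovered outpatients can score 1 or 2. The protocol gives neither the outpatient share nor any category distribution, so both are assumed. Two sets were used, each with 40 per arm and a tie-corrected van Elteren test (the stratified Wilcoxon test) on baseline ≤3 versus >3.

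- Set A: control day-7 probabilities for categories 1 to 7 are .10/.20/.15/.35/.08/.07/.05 for inpatients and .25/.35/.20/.12/.03/.03/.02 for outpatients. 30% of inpatients have baseline ≤3. A proportional-odds shift gives p1 = 0.68 within each setting. 6,000 runs.
- Set B: inpatients on oxygen .03/.12/.15/.45/.12/.08/.05; inpatients without oxygen (35% of inpatients) .15/.40/.25/.14/.03/.02/.01; outpatients .30/.52/.05/.10/.01/.01/.01. Common odds ratio 3.2. 4,000 runs. The recoded column for B also has setting as a stratum.

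| Outpatients | A literal | A recoded | Loss | B literal | B recoded | Loss |
|---|---|---|---|---|---|---|
| 10% | 79% | 81% | 2 | 73% | 80% | 7 |
| 20% | 76% | 80% | 5 | 65% | 78% | 13 |
| 30% | 72% | 81% | 9 | 59% | 80% | 21 |
| 40% | – | – | – | 54% | 80% | 26 |
| 50% | 63% | 81% | 18 | – | – | – |

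Losses are in percentage points, with a simulation standard error of about 1 point. Repeat runs at 30% gave about 8 points for A and 19 to 20 for B. A fair summary is 2 to 7 points at 10% outpatients and 8 to 20 at 30%. Within outpatients alone, set A's true p1 of 0.68 shrinks to 0.57 under literal coding. If every outpatient sat at 3 in both arms, set A would give 78%, 72%, 65% and 50% at 10%, 20%, 30% and 50%.

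**3. Adding setting as a stratum while leaving scores literal.** Under set B, at 10%, 20%, 30% and 40% outpatients, power rises from about 72/65/58/53% to about 76/72/68/64%, a gain of roughly 4, 7, 10 and 11 points (10,000 runs). Under set A the same step adds at most about 1 point. The gain arises when ward patients without oxygen mostly reach 1 or 2 by day 7 while outpatients are held at 3, so that pooling them adds noise; set A does not have that contrast. Once the scores are recoded, a setting stratum adds little: about 1 point or less under B, and up to about 3 points under A.

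**The case against.** Four points count against a stronger version.

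- A reader might infer that outpatients have no category at all. They do: 3, or 4 if on oxygen. What is missing is a category for their recovery.
- A reader might infer that outpatients are tied whatever the treatment does. They are not. An outpatient who needs oxygen or intensive care, is ventilated or dies still moves to 4 to 7, so benefit through prevented worsening stays visible.
- A reader might infer bias between arms, or site-dependent scoring by unblinded staff. A site could score outpatients 1 or 2 by analogy, and the trial is open label, but nothing in the protocol shows that coding differs by site or arm. Setting is balanced by the randomisation, so literal coding dilutes the effect.
- A statistical analysis plan, not shown, could contain a coding rule. That is possible, but the categories are the protocol's own endpoint definition and sites apply them at the visit, so the gap sits in Attachment 2.

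Timing also limits the remedy. The amendment rationale in section 18.1.1 says that 111 patients were already randomised and that no more are planned. New wording cannot change scores already entered, and a site that entered 3 had no reason to record whether normal activities had resumed. This objection stands in part: recoding is retrospective and may be incomplete.

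**Conclusion.** The point holds as a gap in the endpoint definition. Under the literal wording a never-admitted outpatient cannot show improvement below 3 and ranks below a discharged inpatient, and the planned strata do not separate the two groups. The effect is a weakened co-primary comparison.

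Its size is not known. It rests wholly on the assumed outpatient share and day-7 distributions: about 2 to 7 points of power at 10% outpatients, about 8 to 20 at 30%. If few outpatients were enrolled, little is lost. The direction does not depend on which set is used.

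This should be fixed before analysis. It is not critical, because section 11 declares the study explorative and the sample size is based on D-dimer.

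**What to change.** 1. In section 11.2 and the Synopsis, stratify the Wilcoxon test by setting as well as by baseline ≤3 versus >3. Setting is already a randomisation factor, so this needs no new data and no recoding. Under literal coding at 10 to 40% outpatients it recovers roughly 4 to 11 points under set B, but almost nothing under set A, so it does not replace step 2.
2. In Attachment 2, define 1 and 2 as not hospitalised (never admitted or discharged), with and without resumption of normal activities respectively. Define 3 and 4 as hospitalised, non-ICU, without and with oxygen. State how an outpatient on oxygen is scored. Apply this at baseline and at all visits.
3. As no further recruitment is planned, recode never-admitted outpatients from source records, blind to arm, before database lock. Pool 1 and 2 where resumption of normal activities was not recorded; with setting as a stratum, this can be done among outpatients without changing inpatient ranks. Report the analysis of the scores as recorded as a sensitivity analysis.
4. Report the number of outpatients per arm, so that readers can judge how much the coding matters.

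The cost is a wording change in Attachment 2, section 11.2 and the Synopsis, plus a source check limited to outpatients. The downside is some loss of information for those who end in the pooled category, and a score definition that departs from the wording sites used at the visit, which is why the recorded scores should also be analysed.

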### Attachment 3: CKD-EPI Formula

$$eGFR = 141 \cdot \min(Scr/\kappa, 1)^\alpha \cdot \max(Scr/\kappa, 1)^{-1.209} \cdot 0.993^{Age} \cdot 1.018 \text{ [if female]} \cdot 1.159 \text{ [if black]}$$

- Scr is serum creatinine (mg/dL)
- $\kappa$  is 0.7 for females and 0.9 for males
- $\alpha$  is -0.329 for females and -0.411 for males
- min indicates the minimum of Scr/ $\kappa$  or 1
- max indicates the maximum of Scr/ $\kappa$  or 1

## Attachment 4: Secondary efficacy endpoints and other endpoints of interest

All efficacy evaluations and endpoints described in Section 9.2 will be evaluated and adjudicated by the CEC (defined below). Safety endpoints are defined in Section 9.4.

### Secondary efficacy endpoints

1. DVT – displaying signs or symptoms of proximal or distal lower extremity DVT, upper extremity DVT, or other DVT and confirmed by adjudication, based on 1 or more of the following diagnostic criteria:
  1. a non-compressible venous segment on compression ultrasonography, or in patients with a history of previous DVT, either a new non-compressible venous segment or a substantial increase (4 mm or more) in the diameter of the vein during full compression in a previously abnormal segment on ultrasonography, or
  2. the presence of an intraluminal filling defect on venography, or
  3. DVT documented at autopsy.

If in patients with history of previous DVT or incomplete documentation of the previous episode is available, additional criteria may be integrated into the adjudication of the current event, such as: ultrasonography appearance of the thrombus. The totality of available clinical, imaging and laboratory findings should be considered.

2. PE – displaying signs or symptoms suggestive of PE and confirmed by adjudication based on 1 or more of the following diagnostic criteria:
  1. an intraluminal filling defect on CT angiography or spiral CT, or
  2. an intraluminal filling defect on pulmonary angiography or cutoff of a vessel more than 2.5 mm in diameter, or
  3. a perfusion lung scan defect of at least 75% of a segment with corresponding normal ventilation (high probability ventilation-perfusion (V-Q) scan), or
  4. a non-high probability V-Q scan abnormality associated with DVT documented by ultrasonography or venography, or
  5. in the absence of imaging test in a hemodynamically unstable patient, evidence of right ventricular dysfunction by transthoracic or transesophageal echocardiogram (ESC criteria), or
  6. PE documented at autopsy.

The anatomic extent of PE will be classified by the adjudication committee as either segmental or greater, or sub-segmental. The totality of clinical, imaging and laboratory findings should be considered.

3. New myocardial infarction: New Type 1 MI and Type 2 MI. Requires combination of evidence of myocardial necrosis (either changes in cardiac biomarkers or post-mortem pathological findings), and supporting information from clinical presentation, ECG changes or the results of myocardial imaging or coronary artery imaging. The totality of available clinical, ECG and cardiac biomarker should be considered.
4. Ischemic stroke – acute episode of focal cerebral, spinal, or retinal dysfunction caused by infarction of central nervous system tissue.
5. Death will be assigned to 1 of the following:
  1. CV death
    - i) VTE-related: VTE-related death – death due to confirmed PE documented by objective testing or autopsy
    - ii) VTE-related, PE cannot be ruled out – death, which cannot be attributed to a documented cause and for which pulmonary embolism cannot be ruled out (unexplained death)
    - iii) Other CV death
  2. Non-CV death – death not included in 1 of the above categories

6. Progression to intubation and invasive ventilation defined as the use of any instrument penetrating via the mouth (such as an endotracheal tube), nose, or the skin (such as a tracheostomy tube) to serve as an artificial airway.

#### Other endpoints of interest

##### Re-hospitalization for heart failure:

A heart failure event for patients admitted to a hospital and treated as an inpatient should be defined by meeting at least one criterion from each subheading below (biomarker evidence, radiographic or hemodynamic evidence, heart failure symptoms, and intensification of treatment) and/or at least one for heart failure signs.

Biomarker evidence: At least one of the following:

- Brain natriuretic peptide (BNP; e.g.  $\geq 100$  ng/L)
- N-terminal pro-BNP (e.g.  $\geq 300$  ng/L)

Radiographic or hemodynamic evidence: At least one of the following:

- Non-invasive diagnostic evidence of heart failure (e.g. echocardiographic, cardiac MRI)
- Radiographic evidence of pulmonary congestion
- Invasive catheterization with evidence of heart failure (e.g., pulmonary capillary wedge pressure [or LVEDP]  $> 18$  mm Hg, right arterial pressure [or central venous pressure]  $> 12$  mm Hg, or CI  $< 2.2$  L/min per  $m^2$ )

Heart failure symptoms: At least one of the following:

- Dyspnea
- Decreased exercise tolerance
- Fatigue
- Worsened end-organ perfusion
- Other symptoms of volume overload (e.g. swelling of legs, etc.)

Heart failure signs: At least one of the following:

- Peripheral edema
- Increasing abdominal distension or ascites
- Pulmonary rales or crackles, or crepitation
- Increased jugular venous pressure, hepatojugular reflux, or both
- Third heart sound or gallop
- Clinically significant rapid weight gain related to fluid accumulation)

Intensification of treatment: At least one of the following:

- Augmentation of oral diuretic therapy
- Intravenous diuretic or intravenous vasoactive therapy

